PROTOCOL CONCEPT SHEET 2 – PROTOCOL

Compound No. E2007

Name of Active Ingredient: Perampanel

Study Protocol Title

An Open-label, Observational, Prospective, Multicenter Study to Evaluate the Long-term Efficacy and Safety of Perampanel as Monotherapy in Subjects Age 4 Years and Older with Focal Onset Seizures

Investigators

[name] (Principal)

Sites

Approximately 10-15 sites in Japan

Study Period and Phase of Development

From April 2021 to December 2024 (from first patient in to last patient out), including a 12-month enrollment period for 30 months of monotherapy treatment or until perampanel is discontinued, whichever comes sooner

Phase 4

Objectives

Primary Objective

The primary objective of the study is to evaluate 24-month seizure freedom in response to perampanel monotherapy in subjects age 4 years and older with focal onset seizures (FOS) (with or without focal-to-bilateral tonic clonic seizures [FBTCS])

Secondary Objectives

1. To evaluate the treatment effectiveness as measured by pragmatic seizure-free rate in response to perampanel monotherapy at 6, 12, 18 and 30 months

2. To evaluate the treatment effectiveness as measured by sustained seizure freedom in response to perampanel monotherapy at 12 and 24 months

3. To evaluate 6, 12, 18, 24 and 30 months retention on perampanel monotherapy in subjects with FOS

4. To evaluate safety and tolerability of perampanel monotherapy in subjects with FOS over the entire study and the specific time points (month 0-3, 4-12 and 13-30)

5. To evaluate the impact of perampanel monotherapy on the subject's quality of life (QOL) from the baseline to the specific time points (month 1, 3, 6, 12, 18, 24, 30)

Exploratory Objectives

1. To explore the effect of perampanel monotherapy on sleep quality using the HARU-1 wearable device

2. To evaluate the treatment adherence of perampanel

3. To explore clinical factors that influence seizure freedom rate in subjects receiving perampanel monotherapy

Study Design

This is an observational, prospective study in subjects with a diagnosis of FOS (with or without FBTCS), for whom the treating physician has made the decision to initiate perampanel as

monotherapy.

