- For off-site assessments, subjects will be provided with an electronic patient report outcome (ePRO) device and instructed in its use for recording seizure diaries, study drug adherence, and QOL (EQ-5D-5L, VAS and PedsQL). The seizure diaries input can be recorded at anytime when a seizure occurs and the presence or absence of a seizure is confirmed once a month via ePRO device reminder. Study drug adherence and QOL assessments will be performed at 1, 3, 6, 12, 18, 24 and 30 months. For subjects less than 18 years old, family members/caregivers should enter on behalf of the subjects. For sleep substudy, subjectswho have received perampanel monotherapy for at least 3 months after treatment initiation and remain stable at target dose of 4-8 mg/day for at least 4 weeks will have post-baseline sleep measurements taken onceusing the HARU-1 wearable device at any time until Months 12. The data on the time that subjects start trying to sleep and the time they get up in the morning will be recorded using the device by pressing the button on the device.

Subjects who discontinue perampanel because of adverse events or other reasons will be followed up approximately 1 month (+ 2 weeks) after last dose for TEAE/serious adverse event (SAE) follow up and subjects will need to completed ePRO assessment at perampanel discontinuation and 1 month (+ 2 weeks) after.

Number of Subjects

Approximately 60 subjects

Inclusion Criteria

1. Male or female, age 4 years or older at the time of informed consent (in the case of minors, consent from a legal representative [eg, one parent] is required)

2. Diagnosed with FOS (with or without FBTCS) according to International League Against Epilepy (ILAE) 2017 classification

3. Newly diagnosed or recurrent epilepsy. For subjects with recurrent epilepsy, they must have relapsed at least 2 years after the end of the last antiepileptic drug (AED) treatment.

4. Subjects for whom the decision to initiate perampanel has been made, according to the judgment of the investigator

Specific criteria for participating in the sleep substudy

5.1 Subjects age 20 years or older who agree to participate in sleep assessments.

5.2 Subjects who self report a tendency to a poor night's sleep defined as a sSOL of 30 minutes or more, or sWASO of 60 minutes, for at least 3 times a week over the previous month

Exclusion Criteria

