HARU-1 is a palm-sized wearable device with a highly accurate patch-type EEG sensor to measure brain wave activities using multi-channel, stretchable, and user safety electrode sheet. The sensor makes continouous brain wave measurement possible for up to 10 hours. The data are sent automatically via bluetooth to the data center. Total sleep time (minutes of sleep from sleep onset until lights on), sleep efficiency (proportion of total sleep time per time spent in bed), sleep latency (estimated minutes from the time that the subjects attempts to sleep until sleep onset), WASO (minutes of wake from the onset of persistent sleep until lights on) and duration of sleep stage will be recorded.

4. Clinical factors to predict efficacy

Data for clinical factors to predict efficacy will be taken and recorded as medical history at the screening period, which are baseline seizure frequency, age at diagnosis, time since diagnosis, etiology (idiopathic, structural), and epileptic focus. Additionally, seizure freedom status at 3 months will also be considered as clinical factors.

5. Study drug adherence

Adherence on perampanel will be input by subjects using the ePRO device.

Bioanalytical Methods

Not applicable.

Statistical Methods

Data will be analyzed according to the Statistical Analysis Plan (SAP) using SAS or other validated statistical software, as necessary. The data will be fully tabulated with summary statistics for continuous variables and frequency and percent for categorical variables. Graphs, using summary values and individual line plots as appropriate, will be used to describe the data.

Study Endpoints

Primary Endpoint

1. Pragmatic seizure free rate at 24 months

Secondary Endpoints

1. The pragmatic seizure-free rate at 6, 12, 18 and 30 months

2. The sustained seizure-free rate at 12 and 24 months

3. Retention rate at 6, 12, 18, 24 and 30 months

4. Incidence of TEAEs over the entire study and the specific time points (month 0-3, 4-12 and 13-30)

5. Change from baseline in EQ-5D-5L and PedsQL to the specific time points (month 1, 3, 6, 12, 18, 24, 30)

Exploratory Endpoints

1. Change from baseline in total sleep time, sleep efficiency, sleep latency, WASO, and duration of sleep stage at the post-baseline measurement (at least 3 months after treatment initiation and remain stable at target dose of 4-8 mg/day for at least 4 weeks) until Months 12

2. Study drug adherence rate at month 1, 3, 6, 12, 18, 24 and 30

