3. Clinical factors to predict seizure freedom at 3, 12 and 24 months

Analysis Sets

1. The Safety Analysis Set is the group of subjects who received at least 1 dose of perampanel and had at least 1 postdose safety assessment.

2. The Full Analysis Set (FAS) - All subjects who received at least 1 dose of perampanel will be included in the FAS.

Efficacy Analyses

1. For sustained seizure freedom rate: the number (percentage) of subjects with FOS who achieved seizure-freedom throughout the entire specified time period (numerator) as assessed in the FAS (denominator). Kaplan-Meier will be performed for survival analysis.

2. For pragmatic seizure-free rate: the pragmatic seizure-free rate at 6, 12, 18, 24 and 30 months in the FAS (the number of subjects free of all seizures at 6 months [and for the previous 3 months], and free of all seizures at 12, 18, 24 and 30 months [and for the previous 6 months][numerator], as a proportion of the FAS[denominator]). There will be no imputation for missing data – subjects

with missing data or not ongoing on perampanel at 6, 12, 18, 24 and 30 months will be assumed not to be seizure free.

3. For retention rate: the number (percentage) of subjects remaining on perampanel during the specified time period as assessed in the FAS.

Pharmacokinetic, Pharmacodynamic, Pharmacogenomic, and Other Biomarker Analyses Not applicable.

Pharmacokinetic Analyses

Not applicable.

Pharmacodynamic, Pharmacogenomic, and Other Biomarker Analyses

Not applicable.

Safety Analyses

All safety analyses will be performed based on the Safety Analysis Set. Safety will be assessed over the entire study and also at specific timepoints (month 0-3, 4-12 and 13-30).

The TEAE verbatim descriptions (investigator terms from the case report form [CRF]) will be coded to system organ class (SOC) and preferred terms (PT) using the Medical Dictionary for Regulatory Activities (MedDRA). The number (percentage) of subjects with TEAEs and serious adverse events (SAEs) will be summarized by MedDRA SOC and PT. The incidence of TEAEs will be summarized by severity (mild, moderate, or severe). Categorical variables (age range) will be summarized as number (percentage) of subjects by visit. Exposure to perampanel will be assessed by recording perampanel dose at each visit. Discontinuations because of adverse events will be analysed.

Other Analyses

1. QOL:

- Overall QOL will be reported as the change in EQ-5D-5L score from the baseline at each designated time.

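### TEAE incidence in months 4-12 and 13-30 has no at-risk denominator; if the full Safety Analysis Set is the divisor, late-period incidence is understated

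*Protocol*

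**What the plan says.** The Analysis Sets section defines one safety population: subjects who "received at least 1 dose of perampanel and had at least 1 postdose safety assessment". Nothing in that definition depends on being treated or observed later in the study.

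The Safety Analyses section then says "All safety analyses will be performed based on the Safety Analysis Set", and the next sentence extends this to the periods: "Safety will be assessed over the entire study and also at specific timepoints (month 0-3, 4-12 and 13-30"). The statistic is a crude count and percentage: "The number (percentage) of subjects with TEAEs and serious adverse events (SAEs) will be summarized by MedDRA SOC and PT". By-period TEAE incidence is secondary objective 4 and secondary endpoint 4.

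Observation of each subject is limited. The Study Period entry gives "30 months of monotherapy treatment or until perampanel is discontinued, whichever comes sooner", and under Study Design those who discontinue "will be followed up approximately 1 month (+ 2 weeks) after last dose for TEAE/serious adverse event (SAE) follow up". The schedule of assessments gives the same window in weeks (footnote b).

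The safety text names no period-specific subset, no exposure-adjusted rate and no divisor for the period percentages.

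**The concern.** A subject who stops perampanel in month 5 is out of TEAE follow-up well before month 13, yet stays in the Safety Analysis Set. In a months 13-30 table with the full set as divisor, that subject counts in the denominator and cannot count in the numerator. The table then shows at-risk incidence multiplied by the share still at risk, which mixes safety with retention.

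The protocol expects discontinuation: retention at five time points is a secondary endpoint, and discontinuations because of adverse events are to be analysed. Long-term safety by period is a stated objective of a 30-month study, so a late-period figure that looks low partly because subjects have left would mislead on a question the study is meant to answer.

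The periods also last 3, 9 and 18 months. Crude percentages over unequal periods cannot be set against each other, whichever denominator is used.

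**Working it through.** The protocol states no TEAE rate, no expected retention and no period denominator, so there is no figure of its own to reproduce. The check is how the reported percentage depends on the divisor.

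**Inputs**
- N = 60, the approximate target (Number of Subjects). For illustration, all 60 are taken to be in the Safety Analysis Set.
- r = share of the set on drug or within the post-dose follow-up window at the start of the period. Not in the protocol; assumed 40-90%.
- p = TEAE incidence among those at risk. Not in the protocol; assumed 20%, and 40% as a second case.

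**Formulas**
- Percentage on the full set = p × (N × r) / N = p × r.
- Relative understatement = (p − p × r) / p = 1 − r. It does not depend on p or N.

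**Results, N = 60**

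| r | At risk | Full-set figure, p = 20% | Full-set figure, p = 40% | Relative understatement |
|---|---|---|---|---|
| 90% | 54 | 18% | 36% | 10% |
| 80% | 48 | 16% | 32% | 20% |
| 70% | 42 | 14% | 28% | 30% |
| 60% | 36 | 12% | 24% | 40% |
| 50% | 30 | 10% | 20% | 50% |
| 40% | 24 | 8% | 16% | 60% |

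In whole subjects: 8 with a TEAE among 42 at risk is 8/42 = 19.0%; on the full set it is 8/60 = 13.3%. The relative shortfall is 1 − 42/60 = 30%.

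With r = 100% there is no dilution. That is the position at the start of months 0-3, so only the two later periods are affected. Months 4-12 should be affected less than months 13-30, because fewer subjects will have left by then.

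**Unequal lengths.** Take a constant hazard that gives 10% in 3 months, with no dropout. Nine months is three such intervals: 1 − 0.9³ = 27%. Eighteen months is six: 1 − 0.9⁶ = 47%. The underlying rate is unchanged, but the crude percentage rises from 10% to 47%. Duration pushes late percentages up and dropout pushes them down, so the crude figures do not show which way the rate moves.

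**The case against.** The strongest objection is that the protocol never writes the divisor. It names a population on which the analyses are based. A table limited to members of that set who are still observed in a period would also fit the sentence. The sustained and pragmatic seizure-free paragraphs label the FAS as denominator; the safety paragraph has no such label. Period denominators are often fixed in an SAP, and the protocol refers the analysis to one. This stands. A reader might infer that the protocol prescribes dividing the months 13-30 count by all treated subjects; the text does not support that as a written rule.

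Three further points have weight:
- No test or comparison between the three periods is planned, so unequal length is a hazard for the reader of the tables rather than a flaw in a stated analysis.
- Retention is reported separately, so attrition would be visible and a reader could rescale roughly.
- Restricting to those still at risk selects subjects who tolerated the drug, so selective dropout still affects any trend.

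What the objection does not remove is that the protocol gives one positive instruction, a single set for every safety analysis with the periods included, and a crude percentage. An SAP author who follows it without further thought will divide by the full set, and nothing else in the protocol corrects that. Rescaling from retention is only approximate, since retention at month 12 ignores the post-dose follow-up window.

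**Conclusion.** The point holds as a gap in the safety specification whose default reading gives diluted late-period percentages. It does not show that the protocol mandates a biased calculation.

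If the full set is used, the relative understatement in a period is one minus the fraction at risk at its start: 20-50% if 50-80% remain at risk. An at-risk incidence of 40% would then appear as 20-32%. Both the retention range and the incidence are assumptions. The relation itself rests only on subjects past follow-up contributing no TEAEs to the period. If the SAP already restricts each period to subjects still observed, the dilution disappears and only the wording of the protocol needs attention.

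**What to change.** Add to the Safety Analyses section, and carry into the SAP:
- For each period, the denominator is the Safety Analysis Set subjects who are on perampanel or within the post-dose TEAE follow-up window at the start of that period.
- Beside each percentage, give subjects with a TEAE per patient-year at risk in the period. This handles the 3-, 9- and 18-month lengths and also discontinuations within a period, which a start-of-period denominator leaves uncorrected.
- Keep the full Safety Analysis Set as denominator for the whole-study table.
- State that the at-risk figures describe those who stayed on drug and are not evidence of a causal decline in TEAEs over time.

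The cost is a short paragraph and an extra column in the TEAE tables. Dose, treatment status and TEAEs are already recorded at visits, and follow-up is already timed from the last dose, so no new data collection is needed. The downside is smaller denominators, hence less precise late-period percentages, and figures that look higher than on the full set.

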- QOL will be reported as the change in the PedsQL-Generic core scales from the baseline at each designated time. Paired t-test will be performed for significance. To obtain the total scale score, scoring will be done following the PedsQLTM algorithm.
- 2. Total sleep time, sleep efficiency, sleep latency, WASO, and duration of sleep stage
 - The changes from baseline in sleep variables (total sleep time, sleep efficiency, sleep latency, WASO, duration of sleep stage) collected in the HARU-1 device at the post-baseline measurement at any time until Months 12 will be determined. Each variable recorded in the device will be calculated using the data from 1 day or mean of the last 3 days before the visit.
- 3. Clinical Factor to predict efficacy
 - Logistic analysis will be performed. The dependent variable will be seizure free or not seizure free. Baseline seizure frequency, age at diagnosis, time since diagnosis, etiology (idiopathic, structural), and epileptic focus will be assessed individually in univariate analyses; however, all variables will be evaluated using multivariate analyses with forward, backward, or no selection. This analysis is aimed to identify potential predictive clinical factors for achieving seizure freedom or not in subjects with FOS at 3, 12 and 24 months. Additionally, seizure freedom at 12 and 24 months
- 4. Study drug adherence rate

- The number (percentage) of subjects with more than 80%, 50 to 80%, and less than 50% perampanel taken will be summarized. Calculations of adherence are a snapshot of each designated time point (month 1, 3, 6, 12, 18, 24 and 30).

Interim Analyses

Since there is still lack of real world data of perampanel monotherapy, the length of the study, and perampanel LOE approaching soon, we want to make earlier publication. Thus, a total of 2 interim analyses are planned to be conducted. The first interim analyses will be conducted when all subjects have provided 6 months of data and the second one will be conducted when 12 months of data have been provided.

Sample Size Rationale

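### Visit-wise paired t-tests on PedsQL use only subjects still on perampanel at months 6 to 24, so QOL-related dropout can look like a gain

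*Protocol*

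**What the plan says.** QOL is secondary objective 5 and secondary endpoint 5, with change from baseline at months 1, 3, 6, 12, 18, 24 and 30. Other Analyses, item 1, has two bullets. The EQ-5D-5L bullet says "Overall QOL will be reported as the change in EQ-5D-5L score from the baseline at each designated time" and names no test. The PedsQL bullet says "QOL will be reported as the change in the PedsQL-Generic core scales from the baseline at each designated time", followed by "Paired t-test will be performed for significance".

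The study period is "30 months of monotherapy treatment or until perampanel is discontinued, whichever comes sooner". Under Study Design, "Subjects who discontinue perampanel because of adverse events or other reasons will be followed up approximately 1 month (+ 2 weeks) after last dose", and "subjects will need to completed ePRO assessment at perampanel discontinuation and 1 month (+ 2 weeks) after". The schedule of assessments puts month 30 and discontinuation in one shared column and has a separate follow-up column after discontinuation. QOL is marked in both.

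The protocol's one statement on missing data, "There will be no imputation for missing data", stands in Efficacy Analyses, item 2. It concerns the pragmatic seizure-free rate, where subjects who are missing or off perampanel count as not seizure free.

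**The concern.** A paired t-test needs a baseline value and a value at the visit. Subjects who stop perampanel have no QOL value at later planned visits, so each successive test describes a smaller and more selected group. The protocol itself names adverse events as a reason for stopping and makes retention an endpoint, so attrition is expected, and some of it is plausibly related to how subjects feel.

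For seizure freedom the protocol guards against this by keeping every dosed subject in the denominator. The PedsQL test has no such protection. What is at stake is a claim, on a secondary objective, that QOL improves on long-term monotherapy when part or all of the improvement comes from who is left.

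**Working it through.** **Who enters the test.** Planned QOL visits are fixed by date from Day 0 (within 7 days). After stopping, a subject gives a score at discontinuation and one about 1 month later. No rule in the protocol assigns either score to a planned visit. At months 6, 12, 18 and 24 the pairs therefore come from subjects still on perampanel. At month 30 the shared column leaves this open.

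**The plan's own figure.** There is none to reproduce. The protocol gives no SD, expected QOL change or retention, and the target of about 60 is a feasibility figure.

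**Simulation for month 24.** From the protocol: n = 60, baseline and seven later visits. Assumed: SD 15, correlation 0.6 between any two visits, true mean change zero throughout. Dropout at each visit follows logit(p) = a − b × (last observed change / SD). Here b is the rise in log-odds per SD of worsening, and a sets retention (a = −2.3 with b = 1.0 gives 56%). Dropout could start at month 3 in the 85% and 56% rows and at month 6 in the other rows with b above 0.

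| b | Retained at month 24 | Mean apparent gain (points) | False significant gain |
|---|---|---|---|
| 0 | various | 0 | about 2.5% |
| 0.5 | 85% | 0.5 | 4% |
| 0.5 | 67% | 1.1 | 8% |
| 1.0 | 82% | 1.1 | 8% |
| 1.0 | 62% | 2.3 | 18% |
| 1.0 | 56% | 2.9 | 24% |

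The nominal rate for a false gain is 2.5% (the upper half of a two-sided 5% test).

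**Hand check of the two ends.** SD of change = 15 × √(2 × (1 − 0.6)) = 13.4.
- 56% retained: n ≈ 34, SE = 13.4/√34 = 2.30, shift = 2.9/2.30 = 1.26. With critical t = 2.03, P(Z > 0.77) ≈ 22%, close to the simulated 24%.
- 85% retained: n = 51, SE = 13.4/√51 = 1.88, shift = 0.5/1.88 = 0.27. With critical t = 2.01, P(Z > 1.74) ≈ 4%.

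**Month 30.** A separate simulation worked in baseline SD units. It assumed that correlation falls with time, SD of the 30-month change 1.06, retention of 80, 65 or 50%, and b = 0.7 or 1.4. With dropout driven by observed QOL, completers show a gain of 0.07 to 0.33 SD, and a false significant gain occurs in 6 to 41% of studies. With dropout driven by current, unobserved QOL, the gain is 0.10 to 0.43 SD. If the discontinuation score instead stands in for month 30, the gain disappears and the bias becomes −0.01 to −0.12 SD across both kinds of dropout. The reading of the shared column therefore decides the sign.

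**What a likelihood-based longitudinal estimate does (month 30).** When dropout depends on observed scores, the bias falls from 0.07–0.33 SD to 0.00–0.02 SD. When it depends on unobserved current QOL, the bias falls from 0.10–0.43 SD to 0.04–0.21 SD (0.04/0.10 = 0.40; 0.21/0.43 = 0.49), so roughly half remains.

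**The case against.** **The SAP may deal with it.** The protocol defers to an SAP that is not at hand. Missing-data handling, visit windows, multiplicity and the choice of a key time point can properly be left to it, and their absence here is no fault. This much of the objection stands. The test itself was not left to the SAP, however: the protocol names it, and that choice is the point.

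**The scope is narrow.** The t-test sentence is in the PedsQL bullet. A reader might infer that EQ-5D-5L is tested in the same way, but its bullet specifies only a reported change. The point holds for PedsQL alone.

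**Discontinuation scores are collected.** A reader might infer that the plan discards them. The documents do not say so, and at month 30 they may enter through the shared column. That limits the claim at month 30 but does not help months 6 to 24.

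**The large figures need strong selection and heavy loss together.** This is correct. Milder dropout gives 4 to 8%, dropout unrelated to QOL leaves the test at its nominal level, and the effect is smaller at month 12 than later.

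**Seven tests.** A reader might compute 1 − 0.95^7 = 0.30 as the chance of at least one false positive. That requires independent tests, and all seven share a baseline. Under the assumed correlation and no selective dropout the figure is about 23% in either direction, and about 11% for any false gain. This is separate from the selection problem.

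**The consequence is limited.** QOL is the last of five secondary endpoints in an observational study, and retention is reported alongside it, so readers can see the attrition. Seeing it does not correct the estimate.

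**Conclusion.** The point holds for the PedsQL paired t-test at months 6 to 24: it is an analysis of subjects still on drug, and QOL-related dropout biases it towards improvement. Under the assumptions stated, the spurious month-24 gain is about 0.5 to 2.9 points on an SD of 15, with a false significant improvement in about 4 to 24% of studies against 2.5%. The upper end is the adverse case. Retention and the strength of the link between QOL and dropout are not in the protocol, so only a range can be given. The direction at month 30 is undetermined.

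Two stronger readings are not supported. The protocol does not show that the QOL results will be biased, since that requires dropout related to QOL. Nor does a likelihood model remove the bias in general; it does so only when dropout depends on scores already observed.

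**What to change.** Replace the visit-wise PedsQL paired t-tests with one repeated-measures likelihood model for the total score. Baseline and all planned visits are responses and visit is a factor. Use an unstructured covariance, with a simpler fallback stated in advance, because eight occasions in about 60 subjects may not converge (and PedsQL is not given to subjects aged 4 at consent). Report the estimated change with a 95% confidence interval at each visit. If EQ-5D-5L is to be tested, use the same model.

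Keep the observed-case change as supportive. Add a sensitivity analysis using the discontinuation and 1-month follow-up scores, and state whether a discontinuation score counts as month 30.

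The cost is a change of wording and a standard procedure in the planned software, with no new data. The drawback is the missing-at-random assumption: if dropout depends on current QOL that was not observed, about half the bias remains, which is why the sensitivity analysis is needed.
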